10.6.1 Sharps Injuries and Blood Exposures

(Adapted from CDC Emergency Needlestick Information, <http://www.cdc.gov/niosh/topics/bbp/emergnedl.html>):

For sharps / needle stick injuries, and/or blood exposure, study staff should immediately:

1. Wash needlesticks and cuts with soap and water
2. Flush splashes to the nose, mouth, or skin with water
3. Irrigate eyes with clean water, saline, or sterile irrigants
4. Report the incident to site supervisor
5. Seek medical treatment
 - a. Injured staff and/or client may need to seek medical care with local urgent or emergency care for treatment and evaluation for post-exposure prophylaxis
 - b. Contact Clinician Consultation Center (UCSF, <http://nccc.ucsf.edu/>) at [name] (9 a.m. – 2 a.m. EST, seven days a week) for clinical guidance on obtaining Post-Exposure Prophylaxis
6. Complete Adverse Event Reporting Form (**Appendix AN**), enter event details into MS Access database (if event includes a study participant), and notify [name] (FANO) within 24 hours of event.

10.6.2 Fainting and Related Injuries

While unlikely, it is possible that a client or staff could faint during a screening activity. A person experiencing fainting episodes can be triggered by factors or situations such as hypoglycemia, low blood pressure, excessive pain, dehydration, standing for long periods of time, emotional distress and anxiety.

In the event a client or staff faints or is injured during a study activity, study staff should:

1. If possible, assist the client to sit down or lie down on the floor *before* fainting in order to prevent a fall and related injuries.
2. Make sure the client is breathing; sudden cardiac arrest may look similar to fainting

- a. If client is not breathing, or not breathing normally, call 911 and initiate CPR (if appropriate and staff is trained to do so)
3. If necessary (e.g., client has no history of fainting, client was injured during fall, and/or client does not recover consciousness after 2-3 minutes), call 911 to activate local emergency medical system
4. Complete Adverse Event Reporting Form (**Appendix AN**), enter event details into MS Access database (if event includes a study participant), and notify [name] (FANO) within 24 hours of event

10.6.3 Excessive Bleeding

Some clients who participate in a blood screening activity may have a reduced capacity for normal blood clotting (which can be caused by some medications, an underlying health condition, etc.). While excessive bleeding is unlikely to occur as a result of a screening activity, it is important that screening staff are aware of how to identify and respond to a case of excessive bleeding with a client.

1. Apply direct pressure at puncture site (site staff should follow universal precautions, wear gloves, and utilize barrier protections) using available supplies (gauze pads, cotton balls, etc.)
2. Elevate puncture site
3. If bleeding is significant, does not stop, or gets worse, call 911 to activate the emergency response system
4. Complete Adverse Event Reporting Form (**Appendix AN**), enter event details into MS Access database (if event includes a study participant), and notify [name] (FANO) within 24 hours of event

10.6.4 Infection

If a food pantry client or study participant reports an infection that resulted from their participation in a study related screening event, staff should complete an Adverse Event Reporting Form (**Appendix AN**), enter event details into MS Access database (if event includes a study participant), and notify [name] (FANO) within 24 hours of report.

11 Study Compliance

Clinical trials are expensive endeavors and every effort should be made to maximize adherence to the protocol and minimize non-compliance. Comprehensive training on the study protocol, early review of the data, and routine communications with the sites help to minimize protocol deviations. However, protocol deviations do occur, especially in trials such as this one conducted in community settings. There is therefore a mechanism in place to track protocol deviations and procedures and to notify appropriate parties about their occurrence.

Protocol deviations include, but are not limited to the following:

- Randomization of an ineligible participant

- Failure to obtain Informed Consent
- Enrollment of a participant into another diabetes study occurring at the same time
- Wrong treatment administered to participant, such as a participant who is randomized to the waitlist control group and instead receives the intervention
- Outcome measurement not performed, such as follow-up HbA1c or follow-up survey

All protocol deviations should be reported to [name] (FANO) within 48 hours and officially recorded on the Protocol Deviation Log (**Appendix F**). [name] will discuss these deviations with UCSF within 48 hours so that corrective actions may be taken if necessary. While there are rational and expected reasons for occasional deviations, a site with continuous problems is at risk of losing its funding.

12 Data Collection and Study Forms

All survey data collection will be done within the CASIC system, and all study tracking will take place within Microsoft Access databases. Copies of all study forms will be maintained in the MOP for reference. See **Appendix D** for Electronic Forms completed at each study visit.

FAITH-DM is a complex study requiring multiple points of data collection with study participants. Ensuring that all data are collected and properly recorded is critical to study staff being able to accurately analyze results. Research assistants and site staff can use the document “Data Collection Best Practices” (**Appendix AT**) as a guide to consistently maintain quality data collection.

12.1 Source Documentation

A source document is any document on which study data are initially recorded.

Source documents for this study include:

- Screening Log
- CASIC forms
- Healthcare utilization abstraction forms
- Informed consent, HIPAA, and medical records release forms
- Participant compensation receipts
- MS Access database

12.2 Participant Binder

This section describes how participant data are maintained in the study. All essential study documents must be retained at each food bank in a Participant Binder(s) and include the following:

- Signed consent forms
- Paper tracking forms (if any)
- Data correction forms (if any)

12.3 General Instructions for Completing Forms

All data recorded on study forms must be verifiable in the source documents maintained by the food banks. In addition to the Informed Consent, HIPAA, and medical records release forms, additional formats include:

1. CASIC (for survey administration)
2. MS Access database

12.3.1 Best practices for completing paper forms

- **Header:** Complete the header information on **EVERY** page, including pages for which no study data are recorded.
- **Participant ID:** The participant ID must be recorded on **EVERY** page, including pages for which no study data are recorded. Participants must NOT be identified by name on any study document. Use only the participant ID number.
- **Abbreviations:** Use of abbreviations not specifically noted in the instructions for completing the forms can be problematic and should be held to a minimum.
- **Correcting errors:** If an error has been made on the study forms, place a single line through the erroneous entry and record the date and your initials. Indicate the correct response.
- **Skipping items:** Do not skip any items. Some items may carry "Unknown" or "Not Applicable" response choices which should be selected when necessary.
- **Incomplete data:** Data may not be available to complete the form for various reasons. Circle the item for which information is not available and indicate the reason near the appropriate field:
 - If an evaluation was not done, write ND and provide a reason.
 - If the information is not available, but the evaluation was done, write NAV.
 - **Note: Only in rare circumstances, as in the case of lost documentation, should NAV be recorded on the form. Every effort should be made to obtain the information requested.**
 - If an evaluation is not applicable, write NA.
 - **Incomplete or illegible forms:** Incomplete forms that do not have adequate explanation (as described above) compromise the integrity of the entire study. Errors, such as incomplete or illegible forms, are problems that require time and energy to resolve. The use of CASIC helps to prevent these problems.

Incomplete or illegible paper forms:

- If an entire page of the form cannot be completed (e.g., no parts have any responses), and it is unlikely that it will be completed, draw a diagonal line through the form and write NOT DONE, NOT AVAILABLE or NOT APPLICABLE, as appropriate
- The header information must be completed even though no data are recorded on the form
- Do not leave forms incomplete or unused without explanation. Include the explanation on the form itself

12.3.2 CASIC Instructions

CASIC data collection software will be used to record all data from participant baseline and follow-up surveys. CASIC is a secure web-based data collection software hosted on servers at UCSF. To access CASIC via the internet, go to <https://faithdm.ucsf.edu/CASIC/> and sign in using your secure log-in credentials. When internet access is not reliably available, site laptops will be equipped with CASIC Remote. Instructions on how to use CASIC and CASIC Remote follow.

Note: because CASIC is accessible in both online and offline formats for use in completing participant surveys, we will never use paper versions of the participant surveys. Using CASIC exclusively for survey completion will help to maintain consistent, quality data collection, and reduce potential survey administration problems inherent with the use of paper surveys (e.g., correct implementation of the complex skip patterns used throughout the surveys).

Instructions for using CASIC

1. Go to <https://faithdm.ucsf.edu/CASIC/> and log-in
2. Select “FAITH-DM” study
3. From the drop-down menu, select the assessment you wish to administer, the food bank from which the participant was recruited, and the participant ID (from randomization envelop)
4. Begin assessment, being sure to double check accuracy of all information entered
5. Whenever possible, complete survey in single session

Instructions for using CASIC Remote

1. Open CASIC remote from the desktop while internet connection is still available and select “sync” in order to ensure use of the most up-to-date survey (see **section 12.3.2**)
2. In the field, open CASIC remote, log in, and select “Start Assessment”
3. From the drop-down menu, select the assessment you wish to administer, the food bank from which the participant was recruited, and the participant ID
4. Begin assessment, being sure to double check accuracy of all information entered
5. Whenever possible, complete survey in single session
6. When internet connection is reestablished at the end of each day during which data collection took place, click “sync” again to upload all data to the server

For more detailed information regarding CASIC, visit www.westportal.com.

All survey data should be correctly entered into CASIC within **14 days** from survey initiation. Contact UCSF Project Coordinator ([name]) with any CASIC-related questions or issues.

12.3.3 CASIC Remote Syncing Process

Before and after data collection at a field site that may not have reliable internet access, it is best to sync the data on CASIC Remote with the host. Doing so will reconcile all patient survey information so that anything that has been collected using either CASIC online or CASIC Remote will be reflected on both platforms. To sync the data, do the following:

1. Make sure you have adequate internet connection
2. Log onto CASIC Remote using Mozilla Firefox at localhost/CASICRemote/Default.aspx
3. Make sure that the URL in the CASIC Host box is <https://faithdm.ucsf.edu/CASICHost/Services.aspx>
4. Click “Test”
5. Click “Save” or “Continue”
6. Under “Host services” on the left navigation panel, click on “Host URL”
7. Click “Synchronize subject data” in the navigation panel
8. Click “download” to download information from CASIC online and “upload” if you have collected data offline on CASIC Remote in the field and would like to upload to CASIC online

12.3.4 Downloading Updated Instruments in CASIC Remote

Below are the step-by-step instructions for downloading updated instruments in CASIC remote. Note: If you wanted to just updated a single or a few instruments you do not have to do the first part of step 3 (deleting the study). You would want to keep the study and only delete the instruments in question. Contact [name] if you have any questions while trying to do this.

1. Download the updated survey to CASIC Remote
 - a. Step one: log onto CASIC Remote using Mozilla Firefox at localhost/CASICRemote/Default.aspx
 - b. Step two: Under “Host services” on the left navigation panel, click on “Host URL”
 - i. Make sure that the URL in the CASIC Host box is <https://faithdm.ucsf.edu/CASICHost/Services.aspx>
 - ii. Click test
 - iii. Click save (or continue)
 - iv. You must be connected to the internet to do this
 - c. Step three: Click “Study setup” under Host Services.
 - i. Scroll down to Available instruments, delete list of instruments (attached here) from computer
 - d. Step four: On the same page under “Study setup” next to FAITH DM, click “Setup on this computer”
 - e. Step five: Synchronize subject data by clicking “Synchronize subject data” in the navigation panel then clicking “download” to download information from CASIC online and “upload” if you have collected data offline on CASIC Remote in the field and would like to upload to CASIC online. You will do this regularly before and after going to the field for data collection offline.

12.3.5 Paper survey instructions

All participant surveys will be completed electronically using either CASIC online or CASIC remote. Paper surveys will not be used with participants in this study.

12.3.6 MS Access database instructions

This study uses Microsoft Access databases to store tracking information. Specifically, the Microsoft Access database will have the following forms and sub-forms:

- Screening form (for all individuals screened): Screening will be completed on paper forms; study staff is responsible for entering data on each individual screened from paper forms into Access databases at the end of each day.
- Baseline data and participant status form (for all individuals enrolled): This form is completed after initial enrollment of a study participant and is the only form in which study staff can edit participant status.
- Contacts Form: This form will contain all contact information for the participant
- PCP Contact Form: This form will contain all the contact information for a participant's PCP
- Study Data Forms
 - HbA1c form: Record all HbA1c values here
 - Food boxes form: Record all data on participant food box pick-up here
 - Education sessions form: Record all data on participant class attendance here
 - Primary care contact form: Record all data on contact study staff has with primary care here
- Study Data – Browse Only: When study staff need to retrieve, but not edit, data, use this form
- Reports: Study staff use this form to run reports on collected data
- Utilities: This option is used to make changes to the database, such as adding a new interviewer
- Close database: This form safely closes the database

Microsoft Access tracking forms can be used offline and uploaded to the FAITH-DM folder using VPN at the end of each day. It is important that all data is entered each day and securely saved and uploaded to the FATIH-DM folder using the instructions outlines in section 13.1.1.

13 Data Management

It is the food banks' responsibility to ensure that all forms are complete, intact, and transmitted to the Coordinating Center, as appropriate:

13.1 Storage and Transmission of Electronic Files

This section addresses use of the MS Access and CASIC programs for storage and transmission of study data. The UCSF Project Manager will monitor uploads weekly and will contact sites as needed for troubleshooting and quality control / process improvement.

13.1.1 Backing up Microsoft Access Databases to UCSF server

All tracking forms are housed on site-specific Microsoft Access (MA) databases. Each site will have one computer that has the MA database. To prevent data loss, sites will employ the following back-up instructions daily and/or weekly. Though the MA database stored locally on the laptop hard drive will be the “original copy”, study staff must upload a copy of the MA database to the UCSF servers (weekly, at a minimum). Upload the latest version of the MA database to UCSF’s servers using the following process:

Uploading Access information to UCSF server

After you are finished collecting data for the day in Access following these steps:

1. Close the Access database
2. Log in to UCSF Pulse client using your UCSF credentials (the “Pulse” client uses Secure File Transfer Protocol [SFTP] for secure file transfer capabilities between networked hosts)
3. Open your “Public Documents” folder in one window (this is found under Documents → My Documents → Public Documents)
 - a. In this folder you will see the access database you created today. To confirm it’s the correct one, the date modified field to the right of the title should read with today’s date (or whenever you last entered info into it)
4. In a separate window, open the FAITH DM Site Data folder, then open your specific site folder (Houston, Detroit, or Oakland)
 - a. You can do this by right clicking on the FAITH DM Site Data folder and selecting “open in new window”
5. Drag the most recent back end file from the Public Docs folder to the FAITH DM Site Data/Site specific folder
6. Right click on the new file in UCSF’s Site Data folder and rename with today’s date

Alternatively, you can do all of steps 1-3 and instead right click on the most recent Access file in your public documents folder, select “copy” and then open the FAITHDM Site Data/site folder, right click in the folder, and select “paste”. Then rename the file with today’s date.

13.1.2 CASIC Online

1. Go to <https://faithdm.ucsf.edu/CASIC/>
2. Enter User ID and password
3. Select FAITH-DM Study
4. Select study location (food bank name)
5. Select assessment
6. Start survey
7. Questions save every time you click “next”

8. Be sure to click “close window” when done

13.1.3 CASIC Remote

1. Before leaving for field site that may not have internet access, open CASIC Remote and click “sync” to ensure you have the most up-to-date survey and participant list (see **section 12.3.2**)
2. Open CASIC Remote from desktop
3. Log in using User ID and password
4. Select FAITH-DM Study
5. Select study location (food bank name)
6. Select assessment
7. Start survey
8. be sure to click “close window” when done
9. When internet connection is reestablished, upload study data by clicking “sync”

13.2 Administrative Forms

Administrative forms provide documentation of study processes and assist with study operations. Administrative forms for this study include:

- Facsimile Transmittal Sheet - serves as a cover page for all faxes, and must include HIPAA confidentiality language (**Appendix AB**)
- Screening Log - a record of all individuals screened for participation in the study. It should be arranged chronologically and be kept up-to-date at all times (**Appendix B**).
- Participant Identification Code List – a record of the participant's name, ID number, randomization arm, and study entry and exit dates. Due to the confidential nature of this information, it should be maintained only on the encrypted computer, kept in the MS Access Database, apart from other forms and data files at the food bank. The information contained in the list must be maintained by the food bank until 3 years after completion of the study and/or return of the study computer to UCSF.
- Protocol Deviation Log – used to document deviations from the protocol as they are identified by participant, or study staff. This log (**Appendix F**) will be kept and maintained centrally by FANO ([name]).

13.3 Retention of Study Documentation

All study documents should be retained and securely stored for **3 years** following study completion (study completion ends after the end of last data analysis). All study related electronic documents and data sets will be securely stored for **5 years** following study completion, and then deleted.

Best practices for secure document storage:

- Study documents with participant identifying information should be stored separately from documents containing general information or de-identified participant data

- For example, study consent forms and participant baseline forms contain identifying information and should be stored separately from screening logs
- When possible, use permanent markers to black out participant identifying information (e.g., name, DOB) on forms that also contain a participant ID #
- Keep documents organized in 3-ring binders with appropriate tabs
 - Consent forms and baseline forms can be stored by participant last name
 - Forms with de-identified data should be filed in numerical order by participant ID #
- Binders and documents with participant data should be stored in drawers or cabinets that can be secured with a locking mechanism
 - Only FAITH-DM study staff and approved site staff should have access to these storage areas

Once the documentation retention period has passed, all study documents should be destroyed via:

- Document shredding
- Release of documents to secure document disposal service

13.3.1 HCUA Data Stored at Food Bank Sites

As outlined in **section 7.7**, the research assistants (RA) at each site are responsible for requesting, obtaining, storing, and transmitting all HCUA data to the Urban Institute (UI). Transmission of HCUA data (either via mailings of photocopied surveys and records, or via electronic file transfer using secure flash drives) will ultimately result in the existence of two sets of HCUA data (local copies stored at each food bank, and a master copy located at the Urban Institute).

In order to maintain data security, the research assistants at each food bank will destroy all local HCUA data at the conclusion of data collection (projected to be early October, 2017). Prior to destruction of HCUA data, each RA will confirm with Urban Institute project staff that local data collection is complete, and that UI has received all mailings and packages sent by the site RA that include any HCUA data (e.g., completed HCU provider surveys, de-identified medical records, etc.).

Once UI confirms receipt of all HCUA data from a site, the RA will commence with destruction of local HCUA data copies via:

- Document shredding
- Release of documents to secure document disposal service
- Permanent deletion of all electronic files and electronic folders containing any HCUA data

13.4 Data Analysis Plan

13.4.1 Sample size estimation

We used the sampsi program in Stata to calculate the necessary sample size to detect a 0.4% decrease in HbA1c with 90% power. Using our preliminary data from the pilot phase of this project, we projected that the average A1c would decrease from 9.5% to 9.1% with a correlation between the

2 observations per individual at 0.51. Given these parameters, we determined that 300 individuals were needed in both the intervention and waitlist arms of this RCT. In order to allow for 20% attrition from baseline to follow-up, we increased the final recruitment goal to 720 individuals total (240 per site).

sampsi 9.5 9.1, sd1(1.6) sd2(1.9) method(ancova) pre(1) post(1) r1(.51) power(0.9)

Estimated sample size for two samples with repeated measures

Assumptions:

alpha =	0.0500	(two-sided)
power =	0.9000	
m1 =	9.5	
m2 =	9.1	
sd1 =	1.6	
sd2 =	1.9	
n2/n1 =	1.00	
number of follow-up measurements =	1	
number of baseline measurements =	1	
correlation between baseline & follow-up =	0.510	

Method: ANCOVA

relative efficiency =	1.352
adjustment to sd =	0.860
adjusted sd1 =	1.376
adjusted sd2 =	1.634

Estimated required sample sizes:

n1 =	300
n2 =	300

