2.7 Timeline

Timeline

	IRB Finalization, Kick-Off call, distribution of MOP	Hire Research Assistants, Kickoff Meeting	Food Bank Planning, Training	Screening & Enrollment	INT - Food Boxes & Written educational materials distributed	Educational Classes Offered as needed per site	Participant nudges for Control group & intervention group	3-month HbA1c tests	INT Follow-up surveys and HbA1c testing – T6	Control Group Surveys and HbA1c testing – T6	Control Group receives food boxes	Control group final survey and HbA1c testing – T12	Intervention group follow-up HbA1c and survey – T12; HCUS (extension activities)	Target #'s participants recruited this month per food bank	Total Numbers Recruited per food bank	Total Intervention Group at end of the month (Estimate) per food bank	# of participants receiving diabetes food boxes (assuming full participation of control group)	
July 2015	X	X	X															
August	X	X	X															
September			X															
October			X	X	X	X	X							10	10	5	5	
October Notes				Classes ideally offered twice this month														
November				X	X	X	X							20	30	15	15	
December				X	X	X	X	X						25	55	28	28	
January 2016				X	X	X	X	X						25	80	40	40	
February				X	X	X	X	X						25	105	53	53	
March				X	X	X	X	X						20	125	63	63	
April			X	X	X	X	X	X	X	X	X			30	155	73	78	
April Notes			First intervention group concludes; Team Retreat in Houston (4/20-4/21/16); begin sending and retrieving HCU surveys to all PPT providers															
May				X	X	X	X	X	X	X	X			30	185	78	93	
June				X	X	X	X	X	X	X	X			30	215	81	109	
July				X	X	X	X	X	X	X	X			25	240	81	121	
August				X	X	X	X	X	X	X	X	X		20	260	78	131	
August Notes				Screening & enrollment concludes (or earlier if goal #'s are achieved)														
September					X	X	X	X	X	X	X	X	X			66	129	

October					X	X	X	X	X	X	X	X	X			54	127
November					X	X	X	X	X	X	X	X	X			44	122
December					X	X	X	X	X	X	X	X	X			29	109
January 2017					X	X	X	X	X	X	X	X	X			14	94
February					X		X	X	X	X	X	X	X			14	77
February Notes		Final Food Boxes and Group Classes (Intervention Group); send final HCU surveys to both INT & CONT PPTs' Providers															
March							X	X	X	X	X	X	X				67
April							X	X			X	X	X				52
May							X	X			X	X	X				37
June							X				X	X	X				22
July							X				X	X	X				10
August											X	X	X				10
August Notes		Final Food Boxes Distributed (Control Group)															
September												X	X				
October													X				

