- Recruitment-related team conference calls will occur weekly to start, then switch to monthly
- Our goal is to recruit approximately 240 people per site

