All food pantry clients participating in diabetes screening events will be informed by staff that screening results are **NOT** diagnostic. Staff will direct clients to contact their primary medical provider or a community health center to address all personal medical and health questions, and for further screening, evaluation, and treatment as needed. Staff will provide food pantry clients with contact information for local community health care organizations as part of the screening process.

Each food bank site is only expected to conduct regular screening activities until that site reaches its target number of enrolled participants (240 per site). Once study recruitment and enrollment has ended, each site will only be required to continue testing and monitoring enrolled participants per the study timeline. Sites can continue to conduct general screening activities with pantry clients if they have the time, resources, and capacity. However, no new screening information should be tracked in ACCESS after enrollment has closed, and pantry clients screened after the enrollment has closed may not participate in study activities or interventions. Sites can develop their own protocols (e.g.,

referral processes for clients needing care, educational programming, food resources) for managing pantry clients and screening activities beyond what is required for this trial.

When an adult food pantry client provides verbal consent and agrees to participate in a diabetes screening test, we will use the following flow chart to identify what screening tests and procedures are used:

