13.4.4 Statistical analyses

For all the outcomes specified above, we will determine significant improvements using an ANCOVA specification:

$$Y_{i,t=1} = \beta_0 + \beta_1 T_i + \pi Y_{i,t=0} + \varepsilon_i$$

Where $Y_{i,t=1}$ is the given outcome variable measured post-treatment, $Y_{i,t=0}$ is its baseline value, T_i is an indicator for being assigned to treatment, and ε is the error term. Since randomization is at the individual-level, HuberWhite standard errors will be used. β_1 will provide the intent-to-treat effect.

Loss to follow-up

We intend to collect follow-up data on at least 80% of participants. We will conduct a formal missingness investigation to determine if the attrition rate differed between intervention and waitlist groups. If treatment status is found not to significantly affect attrition at the 5 percent significance level, then all estimation will proceed without any adjustment for attrition. If attrition is found to be related to treatment status, we postulate that attrition will be higher for the control group, and will employ Lee bounds to obtain bounds on our treatment estimates which are robust to this attrition (<https://ideas.repec.org/c/boc/bocode/s457477.html>). Multiple imputation for missing outcome data will also be explored as sensitivity analyses (<http://aje.oxfordjournals.org/content/175/3/210.full>).

Per protocol/exposure to treatment

Among those with complete baseline and follow-up A1c ascertainment, we will also examine the influence of the amount of exposure to the program. Specifically, we will determine whether the

participants who met our criteria for being “engaged” in the program (overall and by specific intervention component) had larger effects than those who were less engaged.

In this analysis, because the randomization benefits will be lost, we will adjust for other covariates in our model that we hypothesize to influence A1c and self-management improvements: age, gender, race/ethnicity, educational attainment, language, and site/location.

Subgroup analyses

While we are randomizing within sites, we also plan to conduct subgroup sensitivity analyses by both adjusting for site and examining changes within site to determine differential effectiveness by location. Site-specific differences will be shared with the food banks, but only reported publicly in manuscripts if found to be significantly different.

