13.5.3 Sample size estimation

The health care utilization analysis will utilize the sample generated by the FAITH-DM study. The estimated recruitment goal for the project is 720, with a projected sample size of 600 (300 each in intervention and waitlist arms) after estimated loss to follow-up of 20%. This sample provides the basis for the analysis of the self-reported utilization data and the pool of participants from which provider surveys will be requested. It is our goal to collect provider data from at least 80% of the intervention participants and 70% of the waitlist control participants (it is anticipated that this group will yield fewer primary care provider relationships, since they are not receiving the intervention that supports these). The pilot project upon which this study was based suggested that most individuals who participated in food pantry screening reported that they had a primary care provider at the time of their enrollment in the pilot project. However, prior health records were not requested from those providers in the pilot so it is difficult to know prospectively how many provider contacts will actually yield records, given that individuals struggling with food insecurity may also have been disconnected from health care access in the months prior to their recruitment at the food pantry.

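### 720 enrolled with 20% loss leaves 576 (288 per arm), not the stated 600 (300 per arm); power for 0.4 is then 88.8%, not 90% (minor)

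*Combined protocol and SAP*

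**What the plan says.** Section 13.4.1 gives a Stata calculation for an ANCOVA comparison with one baseline and one follow-up HbA1c. It arrives at 300 per arm for 90% power and then sets the enrolment target: "In order to allow for 20% attrition from baseline to follow-up, we increased the final recruitment goal to 720 individuals total (240 per site").

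Section 13.5.3, in the health care utilization plan, takes the same 720 and reports a "projected sample size of 600 (300 each in intervention and waitlist arms) after estimated loss to follow-up of 20" percent.

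The attrition paragraph of section 13.4.4 sets the follow-up goal: "We intend to collect follow-up data on at least 80% of participants".

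Two operational sections repeat the enrolment target. Section 4 says "Our goal is to recruit approximately 240 people per site", and section 5.1 expects regular screening at each site "until that site reaches its target number of enrolled participants (240 per site"). The timeline in section 2.7 differs. Its column "Total Numbers Recruited per food bank" passes 240 in July 2016 and ends at 260 in August 2016, beside a note reading "Screening & enrollment concludes (or earlier if goal #'s are achieved").

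**The concern.** The figures 720, 20% and 600 in section 13.5.3 cannot all be true. They fit an inflation of 600 × 1.2 = 720, whereas allowing for a 20% loss means dividing by the retained fraction, 600 / 0.8 = 750. The plan writes no inflation formula, so the cause is an inference; the mismatch is not.

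The figure 600 matters because it is the analysed number to which section 13.4.1 attaches 90% power, and section 13.5.3 reuses it as the base for the self-reported utilization analysis and as the pool for provider surveys. Carried into a trial report, it would overstate both the planned sample and the power at the plan's own attrition rate.

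The timeline raises a second, smaller question: whether the target is 240 or 260 per site.

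**Working it through.** **Inputs (section 13.4.1).** Two-sided alpha 0.05; power 90%; means 9.5 and 9.1, so a difference of 0.4; SDs 1.6 and 1.9; baseline to follow-up correlation 0.51; 1:1 allocation; attrition 20%; 720 enrolled at three sites.

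**Step 1: reproduce the plan's 300 per arm.** ANCOVA multiplies each variance by 1 − 0.51² = 0.7399. The relative efficiency is 1 / 0.7399 = 1.352 and the SD factor is √0.7399 = 0.860, giving adjusted SDs of 1.376 and 1.634. All four values match the printed output.

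n per arm = (1.960 + 1.2816)² × (1.6² + 1.9²) × 0.7399 / 0.4² = 299.8, rounded up to 300. The base calculation is correct.

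**Step 2: apply the stated attrition.**

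- Remaining from 720: 720 × 0.80 = 576, or 288 per arm.
- Needed to retain 600: 600 / 0.80 = 750, or 250 per site.
- Loss implied by going from 720 to 600: 1 − 600/720 = 16.7%, that is 83.3% retention.
- Shortfall at 20% loss: 600 − 576 = 24, and 24/600 = 4%.

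**Step 3: effect on power.** With n per arm, SE = √[(1.6² + 1.9²) × 0.7399 / n]. Power for 0.4 is Φ(0.4/SE − 1.96), and the difference detectable with 90% power is 3.2415 × SE.

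| Analysed per arm | Basis | SE | Power for 0.4 | Detectable difference |
|---|---|---|---|---|
| 300 | plan's projection | 0.1234 | 90.0% | 0.400 |
| 288 | 720 enrolled, 20% loss | 0.1259 | 88.8% | 0.408 |
| 312 | 780 enrolled, 20% loss | 0.1210 | 91.1% | 0.392 |

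A noncentral t calculation at 288 per arm gives 88.7%, so the normal approximation is not driving the result.

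**Step 4: could another reading explain 720?** A one-sided test would need 245 per arm, and dropping the ANCOVA adjustment would need 406. Neither reproduces the plan's 300, so the error lies in the attrition step alone.

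**Step 5: the timeline.** The monthly targets per food bank are 10, 20, 25, 25, 25, 20, 30, 30, 30, 25 and 20. They accumulate to 240 in July 2016 and 260 in August 2016. Three sites at 260 make 780, and 780 × 0.80 = 624 (312 per arm), which would leave no shortfall.

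**The case against.** The strongest reply is that these are planning figures and little depends on them. Section 4 says approximately 240 per site, section 13.5.3 calls its numbers estimated and projected, and the 80% in section 13.4.4 is a floor. At 83.3% retention or better, 720 does deliver 600. All of that stands, and it keeps the point minor. It does not rescue section 13.5.3, which projects 600 at a 20% loss, not at something better. Nor is the gap of 24 a matter of rounding to whole sites, since 750 also divides evenly into 250 per site.

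It can also be said that section 13.4.1 never states that 600 remain after attrition, and that its 90% belongs correctly to 300 analysed per arm. That is right. The explicit misstatement is in section 13.5.3; section 13.4.1 supports it by presenting 720 as a sufficient allowance for 20%.

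On the timeline, one can argue that there is only one goal. Sections 4, 5.1 and 13.4.1 all give 240 per site, section 5.1 ties regular screening to reaching that number, and August 2016 may be a contingency month because enrolment can close early. This is a reasonable reading, and 720 is best taken as the operative total. Even so, the timeline sets a monthly target that carries the count to 260 without saying that it is a reserve, so a clarifying line is fair.

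**Conclusion.** The concern holds, as a minor arithmetic error. At exactly 20% loss from 720, the analysed sample is 576 (288 per arm). Power for a 0.4 difference is 88.8%, about 1.2 points below the 90% attached to 300 per arm. The plan's sample size formula and its 300 per arm are sound, and neither the design nor the primary analysis changes. If 260 per site were the real target, the shortfall would disappear.

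The power figures take the plan's inputs as given, with 1.6 and 1.9 as the SDs of the two arms and attrition equal between arms. The documents do not say whether those SDs describe the arms or the pilot's before and after measurements. That is a query, not an error, and the attrition arithmetic does not depend on it. For scale, power at 288 per arm would run from 83.6% (assuming 1.9 in both arms) to 93.7% (assuming 1.6 in both).

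**What to change.** Restate sections 13.4.1 and 13.5.3 along these lines: 720 enrolled; 576 analysed (288 per arm) at 20% attrition; 88.8% power to detect 0.4; 90% power (300 per arm) requires retention of at least 83.3%.

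Reconcile the 240 per site in sections 4, 5.1 and 13.4.1 with the 260 per food bank in section 2.7, for example by marking August 2016 as a contingency month if that is what was meant, and name the total on which the power statement rests. While editing, add a line saying what the two SDs represent.

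The cost is wording in the manual and analysis plan. No extra enrolment, procedure or change of analysis is needed; the stated power falls by about 1.2 points.
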